# Effect of pleuran ( $\beta$ -glucan from *Pleurotus ostreatus*) on the clinical course of patients with chronic rhinosinusitis.

## EPCCOR study

### SUMMARY OF STUDY PROTOCOL

Title of clinical research:	Effect of Pleuran ( $\beta$ -glucan from Pleurotus Ostreatus ) on the Clinical Course of Patients With Chronic Rhinosinusitis.
Acronym:	EPCCOR
Principal investigators:	doc. MUDr. [name].  , [contact], Email: [contact] MUDr. [name]., MPH  [contact], [contact], Email: [contact]
Investigators:	MUDr. [name]  MUDr. [name]  MUDr. [name]  MUDr. [name] 
Investigating sites:	 Department of Pediatric ENT, University Hospital Brno - Children's Hospital, [name]  ORL department, University Hospital Brno, [name]  ORL department, F.D. Roosevelt University Hospital with Policlinic, Banská Bystrica, Slovakia  ORL private practice – Sante s.r.o, [name]  ORL private practice – ORL-HP s.r.o., [name]
Study design:	Multicentre, prospective, randomized, open-label, controlled study with a dietary supplement Imunoglukan P4H® capsules in newly diagnosed patients over 12 years old with chronic rhinosinusitis without nasal polyps.
Project summary:	
Chronic rhinosinusitis (CRS) is a serious and growing health issue. The quality of life of patients with CRS is, in some areas, even worse than that of patients with chronic heart failure, chronic obstructive pulmonary disease, or chronic back pain.
 
A well-functioning immune system is essential for alleviating CRS symptoms and improving disease outcomes. Currently, there is no clinical study evaluating the effect of pleuran (<math>\beta</math>-glucan from Pleurotus ostreatus) in patients with CRS.
 
The primary goal of this clinical research is to learn if Imunoglukan P4H® as an add-on therapy to standard of care treatment according to the EPOS guidelines can help to prevent CRS exacerbations, respiratory tract infections and reduce the use of antibiotics and intranasal corticosteroids

	
(INCS) in newly diagnosed children over 12 years old age and adults with CRS without nasal polyps.
 
The investigational product, Imunoglukan P4H® capsules, will be added to the standard of care treatment according to the EPOS guidelines (INCS and saline irrigation) as prescribed by their treating physician.
 
Patients will be proportionally randomized into two arms:
 
Group A: standard of care treatment with INCS and saline irrigation + Imunoglukan P4H® capsules (IMG® 100 mg + Vitamin C 100 mg) at a dose of 2 capsules once daily for 3 months, then there will be three months follow-up (without Imunoglukan P4H®). This cycle (3-month treatment and 3-month follow-up) will be repeated twice (only participants in the active group).
 
Group B: standard of care treatment with INCS and saline irrigation

Study population:	Newly diagnosed patients over 12 years old with a diagnosis of chronic rhinosinusitis without nasal polyps meeting the inclusion criteria
Inclusion criteria:	
 
• age over 12 years
 
• signed informed consent
 
• patients with newly diagnosed CRS without nasal polyps (meeting the criteria for the definition of CRS according to EPOS)
 
• patients without anatomical abnormalities causing nasal obstruction (nasal septal deformity, nasal turbinate hyperplasia, tumours, craniofacial deformities)
 
• patients able and willing to complete the questionnaires, undergo rhinoendoscopic examination, upper aerodigestive tract swabs and follow-up outpatient examinations
 

Exclusion criteria:	
 
• refused informed consent
 
• inability/unwillingness to complete the questionnaire, undergo rhinoendoscopic examination, upper aerodigestive tract swabs, follow-up outpatient examinations
 
• inability/unwillingness to use the product in accordance with the research protocol and compliance < 75%
 
• patients with protracted rhinosinusitis, exacerbations rhinosinusitis with the presence of an asymptomatic period
 
• patients with CRS during conservative treatment
 
• patients with CRS after previous surgical treatment
 
• patients with grade 3 nasal polyps
 
• patients with adenoid vegetations/persistent pharyngeal tonsils (especially if children are included in the study)
 
• patients with CRS with anatomical abnormalities causing nasal obstruction (septal deformity, turbinate hyperplasia, tumors, craniofacial abnormalities)
 
• patients with significant immunodeficiency
 
• patients with mucociliary transport disorders (e.g. cystic fibrosis, primary ciliary dyskinesia)
 

	
 
• patients taking other immunomodulating preparations regularly and for a long time (e.g. beta-glucans, Preventan, vitamins C and D, probiotics, Echinacea, bacterial lysates, etc.)
 
• pregnant and breastfeeding women
 

Primary endpoints:	
To evaluate the effect of Imunoglukan P4H® capsules as an add-on therapy to the standard of care treatment according to the EPOS guidelines in patients with CRS without nasal polyps on reduction of:
 
 
• number of CRS exacerbations,
 
• use of antibiotics,
 
• use of intranasal corticosteroids,
 
• incidence of respiratory tract infections.
 

Secondary endpoints:	
To evaluate the effect of Imunoglukan P4H® capsules as an add-on therapy to the standard of care treatment according to the EPOS guidelines in patients with CRS without nasal polyps on:
 
 
• severity of CRS,
 
• subjective signs of CRS,
 
• objective signs of CRS,
 
• microbiological cultivation in the upper aerodigestive tract,
 
• safety and tolerability
 

Number of Patients:	
 
• Czech republic: 60 patients enrolled by investigators at 2 centres, randomized into active and control groups (30+30)
 
• Slovakia: 100 patients enrolled by investigators at 3 centres, randomized into active and control groups (50+50)
 

Study Duration:	01.11. 2022 – 31.12. 2025

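### A compliance threshold of 75%, measurable only after randomisation and only in Group A, is listed as an exclusion criterion; applied as such, it would replace the randomised comparison with a selected one

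*Protocol*

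**What the plan says.** All references are to the Protocol, Summary of study protocol.

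- **Exclusion criteria.** One bullet covers "inability/unwillingness to use the product in accordance with the research protocol and compliance", followed by the figure of below 75%.
- **Project summary, Group A.** Patients receive standard care plus capsules "at a dose of 2 capsules once daily for 3 months, then there will be three months follow-up" off product. The cycle is then repeated, in the active group only.
- **Project summary, control arm.** "Group B: standard of care treatment with INCS and saline irrigation". No placebo is mentioned, and no run-in before randomisation.
- **Study design.** "Multicentre, prospective, randomized, open-label, controlled study with a dietary supplement".
- **Number of Patients.** 30+30 in the Czech Republic and 50+50 in Slovakia.
- **Primary endpoints.** Reduction of four outcomes: CRS exacerbations, antibiotic use, INCS use and respiratory tract infections.

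The protocol names no compliance measure for INCS or saline irrigation in either arm. It does not say what happens to a randomised patient who falls below 75%.

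**The concern.** An exclusion criterion should be decidable before allocation, so that it acts alike on both arms. A percentage of capsules taken cannot be known then. It emerges during treatment, and only in patients who were given capsules. If it is used to exclude, Group A becomes a set of patients selected for good compliance, while Group B keeps its counterparts of both kinds.

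Patients who persist with capsules may differ from those who do not in tolerance, in how well they manage their other treatment and in how their disease is going. Those differences would be read as an effect of the product. All four primary endpoints are exposed. If sites also stop following excluded patients, their outcomes are lost and no later analysis can restore them.

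**Working it through.** **1. Is the threshold observable at entry?** The Exclusion criteria and Project summary, side by side:

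| Question | Group A | Group B |
|---|---|---|
| Receives capsules? | Yes, after randomisation | No |
| Placebo? | None mentioned | None mentioned |
| Product compliance measurable before randomisation? | No | No |
| Product compliance measurable afterwards? | Yes | No |
| Can the 75% rule remove a patient? | Yes | No |

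The rule therefore acts after randomisation and on one arm only.

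**2. Arm sizes.** 30 + 50 = 80 per arm, 160 in total. The protocol gives no event rate, effect size or expected compliance, so there is no figure of its own to reproduce. What follows is an illustration under assumed values.

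**3. Apparent rate ratio with no true effect.** Let p be the share of poor compliers (the same in both arms, by randomisation) and k their event rate relative to compliers. Set the complier rate to 1.

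- Group A after exclusion: 1
- Group B, everyone: (1 − p) + pk
- Apparent rate ratio A/B: 1/[(1 − p) + pk]

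For p = 25%:

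- k = 0.75: 1/(0.75 + 0.1875) = 1/0.9375 = 1.07
- k = 1: 1/1 = 1.00
- k = 1.5: 1/(0.75 + 0.375) = 1/1.125 = 0.89
- k = 2: 1/(0.75 + 0.50) = 1/1.25 = 0.80

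Over a wider range of p:

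| p | k = 0.75 | k = 1 | k = 1.5 | k = 2 |
|---|---|---|---|---|
| 10% | 1.03 | 1.00 | 0.95 | 0.91 |
| 25% | 1.07 | 1.00 | 0.89 | 0.80 |
| 40% | 1.11 | 1.00 | 0.83 | 0.71 |

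If all randomised patients are kept, both arms have rate (1 − p) + pk and the ratio is 1.00 for every p and k.

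**4. Chance of a false significant benefit (nominal 2.5%).** This depends heavily on the assumed model, so only ranges are useful. For simulated gamma-Poisson counts (80 randomised per arm, complier mean 1.5 events, Welch test at two-sided 5%, p = 25%), varying the dispersion from 0 to 2 gives:

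- k = 2: roughly 11% to 38%, falling as dispersion rises
- k = 1.5: roughly 7% to 14%
- k = 0.75: below 2.5%

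**5. Loss of precision.** Removing 25% of Group A leaves 60 patients. With equal variances, the variance of the difference rises by the factor (1/60 + 1/80)/(2/80) = 0.02917/0.025 = 1.17, that is by 17%.

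**The case against.** Four points can be made on the other side.

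- **Removal is not stated.** A reader might infer that the protocol orders patients below 75% to be dropped from follow-up or analysis. It does not say so. Analysis populations are commonly left to the SAP, which is not shown and may keep everyone. This limits the claim: removal is implied by the label of exclusion criterion, not laid down separately. The criterion would still conflict with an SAP that kept every patient.
- **The bullet is ambiguous.** Its conjunction could require both conditions. The text does not say what compliance refers to, and the neighbouring bullets are entry criteria, so it might mean compliance expected at screening. On that reading it would act on both arms and do no harm. The reading fits poorly, however: a numerical threshold attached to use of the product cannot be measured before dispensing. Whether both conditions are needed or either suffices, the compliance part is still known only after randomisation.
- **Direction.** A reader might infer that the bias must favour the product. The document does not support this. There is no bias at k = 1, and it reverses if patients stop capsules because they feel well (k below 1). For INCS use, where less is the goal, good compliers may also use more INCS, which would count against the product. This objection stands.
- **Size.** The protocol supports no value of p, k or dispersion. A single false-positive rate would be an artefact of the values chosen. This also stands, which is why only ranges that include k ≤ 1 are shown.

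**Conclusion.** The criterion is wrong as written. On its natural reading it can be observed only after randomisation and can remove patients from one arm only. This is a rule that the protocol itself states, not a detail left to the SAP. If it is applied as an exclusion, the randomised comparison is lost, whichever way the resulting bias runs.

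The bias most plausibly favours the product for exacerbations, infections and antibiotic use. That rests on the assumption that poor compliers have more events, and it may not hold for INCS use. With 25% poor compliers and an inert product, the apparent rate ratio runs from about 1.07 (k = 0.75) to 0.80 (k = 2). These figures show what the rule could do. They do not estimate what it will do in this trial.

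**What to change.** - Delete the 75% compliance condition from the exclusion criteria. Keep only willingness and ability to use the product, judged before randomisation in all patients.
- State that every randomised patient stays in trial follow-up and is analysed in the assigned arm, whatever the compliance.
- Use the 75% threshold only to define a supportive per-protocol analysis, labelled as a non-randomised comparison.

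The cost is a change of wording in the eligibility section and a sentence on follow-up and analysis. The downside is an estimate somewhat diluted by non-compliance. If sites have already excluded patients under this bullet, report how many and at what point, and recover their outcomes where possible.
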